4.5 Interim analyses and data monitoring

4.5.1 Data monitoring committee

An independent data monitoring committee (DMC) will be convened to periodically review and monitor safety data and to advise UCB accordingly. A separate cardiovascular adjudication committee and neuropsychiatric adjudication committee will also review the relevant data for assessment of cardiovascular and potential suicide events respectively, and will provide additional advice to UCB.

The detailed role, scope, responsibilities and complete procedures as well as the identity of the DMC members will be described in a separate DMC Charter. The DMC procedures will ensure that data remain blind to the study team and Investigators at all times during the conduct of the

study. The details regarding the outputs to be produced and the analyses to be performed for the DMC review will be provided in a separate DMC SAP.

A separate Charter will be written for each of the cardiovascular and neuropsychiatric adjudication committees.

4.5.2 Interim analysis

No formal interim analysis will be performed; however interim data cuts will be performed and evaluated. Please refer to the interim SAP for details on the timings and deliverables of these data cuts.

4.6 Multicenter studies

Individual center results will not be displayed.

4.7 Multiple comparisons/multiplicity

Not applicable.

4.8 Use of an efficacy subset of subjects

Not applicable.

4.9 Active-control studies intended to show equivalence

Not applicable.

4.10 Examination of subgroups

Not applicable.

5 STUDY POPULATION CHARACTERISTICS

5.1 Subject disposition

The number and percentage of subjects who were randomized into the study, subjects who completed (which includes those who entered the extension study at Week 36) or prematurely discontinued the study, as well as the reason for discontinuation will be presented by treatment group and for all subjects, based on the RS. The tabulation will also include the number and percentage of subjects who achieved a PASI25 response (for at least one post-Baseline visit), the number and percentage of subjects who relapsed, and the number and percentage of subjects entering the extension study prior to Week 36.

The number and percentage of subjects who discontinued due to AEs will be separately summarized by treatment group and for all subjects, based on the RS.

The number and percentage of subjects included into each of the analysis sets will be summarized by treatment group and for all subjects based on all subjects screened. Percentages will be based on the RS for the purpose of this summary.

Finally, screen failure reasons will be summarized, based on all subjects screened. A listing of subjects who did not meet study eligibility criteria (including glossary) will also be presented.

A subject who completed the study is defined as follows:

- All subjects not enrolling in the extension study will be regarded as completers if they continue in the current study (PS0016) until Week 28 (ie, and completed the Week 28 visit).
- From Week 20 through Week 28, subjects who were previously PASI25 responders but subsequently relapse will undergo the study assessments for that visit (ie, Week 20, Week 24 or Week 28) before receiving the first dose of IMP in the extension study. Subjects may also enter the extension study after the SFU Visit at Week 36. All subjects eligible for the extension study must have the assessment for SFU conducted prior to entering the extension study.

Thus, a subject entering the extension study is regarded as completing PS0016 if they have completed the last visit (ie, Week 20, Week 24 or Week 28) up to the point of entering the extension study.

In addition, the following listings will be presented by treatment group:

- Subject disposition (all subjects screened [ES])
- Study discontinuation (RS)
- Visit dates (SS)
- Subject analysis sets (all subjects screened [ES])

The listing of subject disposition will include the date of informed consent, date of randomization, date and time of first and last dose of IMP (in PS0016), date of premature termination (and primary reason) and date of final contact. The listing will also flag any subjects who entered the extension study, including the visit at which this occurred (ie, Week 20, Week 24, Week 28 or Week 36). If applicable, the date and reason for premature unblinding will also be included.

The listing of study discontinuation will include the reason for discontinuation and the total days on IMP.

The number of days on IMP will be calculated as follows:

$$\text{No. days on IMP} = (\text{Date of Last Dose Received} - \text{Date of First Dose Received}) + 1 \quad [4]$$

5.2 Protocol deviations

Important protocol deviations will be identified and classified by the deviation types listed in the protocol deviation specification document. A listing of all important protocol deviations will be presented for all subjects in the RS and will include the deviation type and description. The number and percentage of subjects with important protocol deviations will be summarized by treatment group and for all subjects for each deviation type, based on the RS.

6 DEMOGRAPHICS AND OTHER BASELINE CHARACTERISTICS

6.1 Derivation of variables

6.1.1 Calculation of body mass index

The BMI in kg/m² is calculated based on the height (in m) and the weight (in kg) using the following formula:

$$BMI = Weight / (Height)^2 \quad [5]$$

The BMI will be reported to 1 decimal place.

6.1.2 Classification of age categories

Age will be classified into categories based on requirements for European Union Drug Regulating Authorities Clinical Trials (EudraCT) and clinicaltrials.gov reporting.

For the EudraCT reporting, the categories will include:

- 18 to <65 years
- 65 to <85 years
- ≥85 years

For the clinicaltrials.gov reporting, the categories will include:

- ≤18 years
- 19 to <65 years
- ≥65 years

6.1.3 Duration of disease

The duration of disease will be calculated as follows and will be presented in years to 1 decimal place:

$$Duration = [(Date\ of\ Screening - Date\ of\ Diagnosis) / 365.25] \quad [6]$$

In the event that the date of diagnosis is incomplete, it will be imputed to the most recent feasible date:

- If only the day is missing, it will be imputed to the last day of the known month
- If the day and month are missing, it will be imputed to December 31 in the known year
- If the date of diagnosis is completely missing, the duration of disease will not be calculated

6.2 Demographics

A by-subject listing of Baseline demographic characteristics will be presented by treatment group. This will include the year of birth (if available), age (in years), sex, race, ethnicity, height (in cm), weight at Screening (in kg) and BMI for all subjects screened. The age will be directly entered into the study database and will not be re-calculated for the statistical analysis.

All Baseline demographic characteristics (with the exception of year of birth) will be summarized by treatment group and for all subjects based on the SS. The summary of age will include descriptive statistics and categorical summaries, the latter based on requirements for EudraCT and clinicaltrials.gov reporting.

The tabulation will be repeated for the FAS, only if the SS differs from the FAS.

Childbearing potential will be listed for the SS.

6.3 Other Baseline characteristics

The following Baseline characteristics will be presented in a by-subject listing for the SS:

- *Duration of disease (including date of diagnosis)
- *Percentage BSA involvement
- *PASI total score
- IGA score
- *HADS-A and HADS-D scores
- Previous use (ie, those therapies classified as past medications) of biologic therapy (Yes/No)

Baseline for each variable (where applicable) is defined in [Table 3–1](#).

The Baseline characteristics listed above will be summarized using descriptive statistics (for continuous variables only*). The IGA score will be summarized including the number and percentage of subjects with each specific IGA score. The previous use of biologic therapy (Yes/No) will be summarized using number and percentage of subjects. Previous use of biologic therapies will be listed as part of the past medications for psoriasis ([Section 6.5.1](#)) and will be confirmed at the DEM.

The tabulation will be presented by treatment group and for all subjects based on the FAS.

6.4 Medical history and concomitant diseases

Medical history will be listed for the RS and summarized for the SS by treatment group and overall, MedDRA system organ class (SOC) and preferred term (PT). The reported term will be included in the listing. The summary will include the number and percentage of subjects, and will be sorted alphabetically by SOC and by descending incidence of PT within each SOC, based on the 'All Subjects' column. A glossary of all medical history conditions will be presented for the RS including the SOC, PT and reported term.

Procedure history will be listed separately by treatment group for the procedure reported term based on the RS.

Concomitant medical procedures performed during the study will be listed for the RS.

6.5 Past, prior, and concomitant medications

Past, prior and concomitant medications will be listed for the RS by treatment group and subject and summarized for the SS by WHODD Anatomical Main Group (Level 1), Pharmacological Subgroup (Level 3) and PT. Tabulations will be presented by treatment group and for all subjects, with separate tabulations for prior (excluding past psoriasis medications) and concomitant categories. Concomitant medications will further be classified into 'Treatment Period' and 'Post-Treatment Period' medications as described in [Section 6.5.4](#).

Past medications for the treatment of psoriasis (based on the information recorded on the psoriasis treatment history page of the case report form [CRF]) will be listed and tabulated separately. The listing will include the treatment name, treatment type (non-biologic systemic agent, biologic agent, phototherapy or photochemotherapy, topical prescription or non-prescription therapy, other) and reason for discontinuation. All other past medications will be summarized together with the prior medications.

All tabulations (excluding past psoriasis medications) will be sorted alphabetically by Level 1 term, alphabetical Level 3 term within Level 1 and decreasing frequency of PT in the 'All Subjects' column. For past psoriasis medications the tabulations will be presented by treatment type as these medications will not be coded.

A glossary of all past, prior and concomitant medications will be presented for the RS including the Anatomical Main Group (Level 1), Pharmacological Subgroup (Level 3), PT and reported term.

6.5.1 Past medication definition

Past medications will include any medications that started and stopped prior to the first administration of IMP. Past medications are therefore a subset of prior medications and include any prior medication with a stop date prior to the date of first administration of IMP. Any medications recorded on the psoriasis treatment history page of the CRF will be considered as past medications.

6.5.2 Prior medication definition

Prior medications include any medications that started prior to the date of administration of the first dose of IMP. This includes medications that started prior to dosing and continued after.

6.5.3 Concomitant medication definition

Concomitant medications are medications taken at least 1 day in common with the study Treatment Period.

Any medication that started prior to dosing and continued after dosing will therefore be classified as both prior and concomitant. Such medications will therefore be counted in tabulations for both prior and concomitant categories.

Any medications with missing dates and/or times will be handled as described in [Section 4.2.4](#) in order to classify them as prior or concomitant.

6.5.4 Classification of concomitant medications

In order to allow for a comparative period across all subjects for incidence of concomitant medication usage, prior to the point at which subjects are eligible to enter the extension study, concomitant medications will be classified as follows:

- **Treatment Period medications:** all concomitant medications taken at least once from the time of the first administration of IMP up until the Week 20 visit. Any medications taken on the date of the Week 20 visit will be included (ie, the cut off will be assumed to be at 23:59 hours on the date of Week 20). Such medications will be designated as ‘Treatment Period’ medications in the tabulations. This will include medications that start prior to the Week 20 visit and are ongoing. Any subjects that withdraw prior to Week 20 will have Treatment Period medications cut off at 140 days relative to the first dose (ie, equivalent to 20 weeks).
- **Post-Treatment Period medications:** all concomitant medications with a start date/time after the Week 20 visit will be designated as ‘Post-Treatment Period’ medications in the tabulations. Thus, Post-Treatment Period medications will include only those medications for subjects not entering the extension study at all or those medications for subjects who enter the extension study at a later visit. For subjects that withdraw prior to Week 20, Post-Treatment Period medications are classified as those starting after 140 days relative to the first dose (ie, equivalent to 20 weeks).

7 MEASUREMENTS OF TREATMENT COMPLIANCE

Overall compliance will be examined in terms of completed injections, where 1 dose consists of 2 sc injections.

This will be calculated as follows and will be presented to 1 decimal place in the listings:

$$\text{Overall compliance (\%)} = [100 \times (\text{Total number of completed injections} / \text{Total number of expected injections})] \quad [7]$$

The total number of expected injections will be derived relative to the date of premature discontinuation for subjects who do not complete the treatment period. For a subject completing the treatment as per protocol, the total number of expected injections is 6 (ie, 2 injections at each of Baseline, Week 4 and Week 16).

The calculated overall compliance will be listed by treatment group and subject, and summarized by treatment group, based on the SS. The summary will include both descriptive statistics for overall compliance (n, mean, SD, median, minimum and maximum) and the number and percentage of subjects based on the following classifications:

- Compliance $\leq 75.0\%$
- Compliance $> 75.0\%$

All data regarding IMP administration will be listed as described in [Section 11.1](#).

8 EFFICACY ANALYSES

8.1 Statistical analysis of the primary efficacy variable

The primary efficacy variable is the change from Baseline in PASI at Week 28.

8.1.1 Derivations of primary efficacy variable

The PASI is the most commonly used assessment for grading the severity of psoriasis in clinical studies and quantifies the severity and extent of the disease and weighs these with the percentage of BSA involvement. The body is divided into four regions comprising the head (h), upper extremities (ue), trunk (t), and lower extremities (le). In each of these regions, the total surface area-of-involvement (A) is graded on a scale of 0 to 6 (0 for no involvement up to 6 for 90% - 100% involvement). The body regions and associated BSA are presented in Table 8–1.

Table 8–1: Body regions for calculation of percent BSA for PASI

Body region	Details of region	BSA	Area-of-involvement of body region (A) ^a
Head (h)	Face, back of head	10%	0 to 6
Upper limbs (ue)	Left, right, upper lower, flexor surface, extensor surface	20%	0 to 6
Trunk (t)	Front, back, groin	30%	0 to 6
Lower limbs (le)	Left, right, upper lower, flexor surface, extensor surface, including buttocks	40%	0 to 6
Total		100%	

A=area-of-involvement score; BSA=body surface area; PASI=Psoriasis Area and Severity Index

^a Where 0=none; 1=1% to <10% affected, 2=10% to <30% affected, 3=30% to <50% affected, 4=50% to <70% affected, 5=70% to <90% affected, 6=90% to 100% affected.

Scoring of psoriatic plaques for the PASI is based on 3 criteria: redness (R), thickness (T), and scaliness (S). Severity is rated for each index (R, T, S) on a scale of 0 to 4 (0=none, 1=slight, 2=moderate, 3=marked, and 4=very marked).

The various body regions are weighted to reflect their respective proportion of BSA. The composite PASI score is then calculated by multiplying the sum of the individual severity scores (R, T and S) for each region by the weighted area-of-involvement score (A) for that respective region, and then summing the 4 resulting quantities as follows:

$$\text{PASI} = 0.1x[(Rh + Th + Sh)xAh] + 0.2x[(Rue + Tue + Sue)xAue] + 0.3x[(Rt + Tt + St)xAt] + 0.4x[(Rle + Tle + Sle)xAle] \quad [8]$$

The following rules will be applied in the calculation of the PASI score in case of missing data:

- If 1 or 2 severity measurements are missing for a certain region (eg, head), the average of the remaining measurements within that region will be utilized to substitute the missing values
- If the area of affected skin and/or all severity measurements for 1 or 2 regions are missing, then the missing (R+T+S)×A for a region will be substituted by the average of the available (R+T+S)×A across the remaining regions
- If the PASI assessment has more missing data than indicated above, at a given visit, then the PASI will be set to missing for that visit

The highest potential PASI score is 72 for severe disease; the lowest score is 0 which indicates no psoriatic lesions are present. The PASI scores are considered as a continuous variable and will be calculated and presented to 1 decimal place in the listings. The percentage improvement in PASI score from Baseline will be calculated as follows:

Percentage improvement from Baseline = $100 \times [(Baseline\ PASI - PostBaseline\ PASI) / Baseline\ PASI]$ [9]

Thus, for subjects with an improvement in the PASI score, the percentage will be positive. For subjects with a worsening in the PASI score, the percentage will be negative.

8.1.2 Primary analysis of the primary efficacy variable

The individual scores for the PASI for each body region (redness, thickness and scaliness severity scores and area-of-involvement score [A]), and the derived total PASI score (from 0 to 72) will be listed for each subject and visit. The listing will include the change from Baseline and percentage change from Baseline for the total score only.

Descriptive statistics (including 95% CI) will be presented by treatment group and visit for absolute values, changes from Baseline and percentage change from Baseline (based on the total PASI score only). For the purpose of the tabulations the lower and upper 95% confidence limits will be truncated as follows:

- For the absolute values the lower 95% confidence limit will be truncated at 0 and the upper 95% confidence limit will be truncated at 72
- For the changes from Baseline the lower 95% confidence limit will be truncated at -72 and the upper 95% confidence limit will be truncated at +72
- For the percentage change from Baseline the upper 95% confidence limit will be truncated at +100%, there will be no truncation of the lower 95% confidence limit

The following figures will be presented:

- Combined individual (spaghetti) plots displaying percentage change from Baseline in PASI score versus time (visit) by treatment group (all subjects will be overlaid on the same plot with separate plots for each treatment group)
- Mean (with 95% CI) percentage change from Baseline in PASI score versus time (visit) by treatment group (both treatment groups will be overlaid on the same plot)

All tabulations and both individual and mean figures will be presented using the FAS and repeated for the PPS (if it differs from the FAS). All listings will be presented using the SS.

For subjects that discontinue the study or those that enter the extension study, missing data will be imputed using LOCF as described in Section 4.2.1.1 for the tabulations and mean figures.

Separate tables and mean figures will also be created based on the observed cases only. Missing data will not be imputed for the listings or the individual figures.

8.2 Statistical analysis of the secondary efficacy variables

The secondary efficacy variables are:

- PASI75, PASI90 and PASI100 response at Week 16

- IGA response (Clear or Almost Clear with at least a 2 category improvement from Baseline) at Week 16

The analysis of the secondary efficacy variables will be based on the FAS for all tabulations and figures. Listings will be based on the SS.

8.2.1 Psoriasis Area and Severity Index response variables at Week 16

The PASI75, PASI90, and PASI100 responses are based on at least 75%, 90%, and 100% improvement from Baseline in the PASI score. Thus, the following will apply:

- If the percentage improvement is $\geq 75\%$ then the subject is a PASI75 responder
- If the percentage improvement is $\geq 90\%$ then the subject is a PASI90 responder (and is a PASI75 responder also)
- If the percentage improvement is 100% then the subject is a PASI100 responder (and is a PASI75 and PASI90 responder also)

The number and percentage of subjects achieving a PASI75, PASI90, and PASI100 response at Week 16 will be tabulated by treatment group. The 95% CI for the percentage of responders will be calculated using a Wilson approximation and included in the tabulation. For the purpose of the tabulation the lower and upper 95% confidence limits for the percentage of responders will be truncated at 0 and 100% respectively.

Missing data will be imputed using NRI as described in [Section 4.2.1.1](#). Subjects with missing data at Week 16 will be regarded as nonresponders for the PASI75, PASI90, and PASI100 variables. This will also be presented using observed cases. Missing data will not be imputed for the listing.

The individual PASI scores will be listed as described in [Section 8.1.2](#). Subjects achieving a PASI75, PASI90 and PASI100 response at each visit will be flagged in the listing.

8.2.2 Investigator's Global Assessment Response at Week 16

A static IGA for psoriasis will be used to assess disease severity in all subjects during the study. The Investigator will assess the severity of psoriasis using a 5-point scale ([Table 8–2](#)).

Table 8–2: Investigator's Global Assessment

Score	Short Descriptor	Detailed Descriptor
0	Clear	No signs of psoriasis; post-inflammatory hyperpigmentation may be present
1	Almost clear	No thickening; normal to pink coloration; no to minimal focal scaling
2	Mild	Just detectable to mild thickening; pink to light red coloration; predominately fine scaling
3	Moderate	Clearly distinguishable to moderate thickening; dull to bright red, clearly distinguishable to moderate thickening; moderate scaling
4	Severe	Severe thickening with hard edges; bright to deep dark red coloration; severe/coarse scaling covering almost all or all lesions

A clinical response with regard to the IGA is defined as clear (0) or almost clear (1) with at least a 2-category improvement from Baseline.

The results of the IGA will be listed by subject and visit. Subjects achieving a clinical response at Week 16 will be flagged in the listing.

The number and percentage of subjects achieving an IGA response at Week 16 will be summarized by treatment group. The 95% CI for the percentage of responders will be included, calculated using a Wilson approximation. For the purpose of the tabulation the lower and upper 95% confidence limits for the percentage of responders will be truncated at 0 and 100% respectively.

Missing data will be imputed using NRI as described in [Section 4.2.1.3](#). Subjects with missing data at Week 16 will be regarded as nonresponders for the analysis. Missing data will not be imputed for the listing.

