### **3 STUDY OBJECTIVES**

#### **3.1 Primary objective**

The primary objective of this study is to evaluate the time-course of PASI over a 28-week period following the administration of bimekizumab given at Baseline and Week 4 to subjects with moderate to severe chronic plaque psoriasis.

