l Includes evaluation of signs and symptoms of active TB and risk for exposure to TB.

m It is recommended that the QuantiFERON TB GOLD test be performed.

[figure not shown]
n All blood samples taken prior to dosing.

o Lesional and nonlesional biopsies to be obtained at Baseline and Week 8. Lesional biopsies to be obtained at Week 16 and Week 28.

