### 5.4 Rationale for study design and selection of dose

PS0016 is a Phase 2a, a multicenter, randomized, subject-blind, investigator-blind study to evaluate the PD, PK, and safety of bimekizumab in adult subjects with moderate to severe chronic plaque psoriasis Treatment Period (28 weeks) and a SFU Period (20 weeks after the last dose of study medication).

The inclusion criteria are designed to ensure all subjects have moderate to severe disease activity. Some exclusion criteria are intended to eliminate subjects who may present an unacceptable safety risk were they to participate in this investigational study program. The full list of inclusion and exclusion criteria is provided in [Section 6](#).

The study will evaluate 2 regimens of bimekizumab to understand the time course of PASI response following sc administration of bimekizumab:

- Treatment arm A: Bimekizumab 320mg at Week 0 and 4 administered sc, placebo administered at Week 16
- Treatment arm B: Bimekizumab 320mg at Weeks 0, 4, and 16 administered sc

The dose level and regimens were chosen based on the efficacy and safety data from the 3 completed clinical studies of bimekizumab (UP0008, RA0124, and PA0007). The selected dosage regimens will in maximum likelihood provide information to evaluate the time-course of PASI response following administration of bimekizumab treatment in this patient population.

All the subjects in the study will receive 320mg of bimekizumab as a sc injection at Baseline and Week 4. Based on our current understanding of PKPD of bimekizumab this will enable maximum PASI response in the subjects. Subjects will then be administered either placebo (Treatment arm A) or 320mg of bimekizumab at Week 16 (Treatment arm B), in order to evaluate the change in time course of PASI response. The proposed doses are expected to be safe since doses greater than 320mg (ie, up to 640mg) have been previously tested, via intravenous administration, in the development of bimekizumab and were found to be safe and well tolerated.

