### **8.7 Week 16 (+/-3 days)**

The following procedures or assessments will be performed prior to administration of study drug:

- Body weight
- Vital signs (blood pressure, pulse rate, and temperature)
- C-SSRS
- HADS
- Record 12-lead ECG
- PASI
- IGA
- BSA
- Obtain blood sample(s) for:
  - Standard safety laboratory tests (hematology and biochemistry)
  - Bimekizumab plasma concentration
  - Anti-bimekizumab antibodies
  - Cytokines, complement, candidate biomarker analysis, and flow cytometry
  - RNA, proteins, and metabolites biomarkers
- Obtain urine sample for:
  - Standard safety laboratory tests
  - Urine pregnancy test for women of childbearing potential
- Obtain skin biopsy (lesional)
- Concomitant medications
- Record AEs
- Contact the IXRS
- Study medication administration (after all other visit assessments completed)

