8.3.1 Psoriasis Area and Severity Index

The absolute values and percentage change (improvement) from Baseline in the PASI score will be summarized as described in [Section 8.1.2](#).

The PASI25 and PASI50 responses are based on at least 25% and 50% improvement from Baseline in the PASI score. Thus, the following will apply:

- If the percentage improvement is $\geq 25\%$ then the subject is a PASI25 responder
- If the percentage improvement is $\geq 50\%$ then the subject is a PASI50 responder (and is a PASI25 responder also)

The definitions of PASI75, PASI90 and PASI100 response are provided in [Section 8.2.1](#). Subjects meeting the definition for PASI75, PASI90 and PASI100 response are also considered as PASI25 and PASI50 responders at the respective visit.

The number and percentage of subjects achieving a PASI25, PASI50, PASI75, PASI90 and PASI100 response will be tabulated by treatment group and visit. The 95% CI for the percentage of responders will be calculated using a Wilson approximation and included in the tabulation. In addition, the percentage of responders (including 95% CI) will be plotted at each post-Baseline visit for each response variable. Separate plots will be presented for each of PASI25, PASI50, PASI75, PASI90 and PASI100 with both treatment groups overlaid on the same plot

Missing data will be imputed using NRI as described in [Section 4.2.1.1](#). Subjects with missing data will be regarded as nonresponders for each of the response variables. Missing data will not be imputed for the listing.

The tables and figures for PASI response variables will also be repeated using observed cases and will include a category for missing data; subjects who enroll in the extension study or those who discontinue will be counted in the missing category for this tabulation where applicable. For this tabulation based on observed cases the denominator for the percentage of responders and nonresponders will be the number of subjects with nonmissing data at the visit.

The individual PASI scores will be listed as described in [Section 8.1.2](#). Subjects achieving a PASI25 and PASI50 response at each visit will be flagged in the listing.

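### Both arms are on one regimen until the Week 16 injection, but the SAP reports efficacy and flow cytometry up to then by arm only, so the most precise estimate is never printed

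*SAP*

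**What the plan says.** **Treatment up to Week 16.** Protocol 5.4: "All the subjects in the study will receive 320mg of bimekizumab as a sc injection at Baseline and Week 4". The arms separate only at the Week 16 injection, which is placebo in arm A and bimekizumab in arm B.

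**Timing of the Week 16 measurements.** Protocol 8.7, whose list includes PASI, IGA, BSA and the blood samples, begins: "The following procedures or assessments will be performed prior to administration of study drug". A footnote to Protocol Table 5-1 adds: "All blood samples taken prior to dosing". Flow cytometry is sampled at Baseline, Weeks 8, 12 and 16, and Week 36/SFU.

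**Objective.** The primary objective (Protocol 3.1) is to "evaluate the time-course of PASI over a 28-week period following the administration of bimekizumab given at Baseline and Week 4".

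**How results are displayed.**
- PASI course, SAP 8.1.2: "Descriptive statistics (including 95% CI) will be presented by treatment group and visit for absolute values", and likewise for changes from Baseline.
- PASI75/90/100 at Week 16, SAP 8.2.1: "The number and percentage of subjects achieving a PASI75, PASI90, and PASI100 response at Week 16 will be tabulated by treatment group".
- IGA response at Week 16, SAP 8.2.2: "The number and percentage of subjects achieving an IGA response at Week 16 will be summarized by treatment group".
- PASI response at every visit, SAP 8.3.1: "response will be tabulated by treatment group and visit".
- Flow cytometry, SAP 9.2: by treatment group, with 95% CIs.

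SAP 3.6 allows an overall column where applicable and points to Table 14-1, which leaves All Subjects blank for the efficacy and pharmacodynamic rows.

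**The concern.** Randomisation assigns no difference in treatment before the Week 16 injection. Every by-arm summary up to predose Week 16 therefore splits one treated population of about 45 into parts of 30 and 15. All four secondary efficacy endpoints (PASI75, PASI90, PASI100 and IGA response at Week 16) are affected. So are the Week 2 to Week 16 part of the PASI course and three of the four post-Baseline flow cytometry visits.

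Two things are at stake. First, the response after doses at Baseline and Week 4 is reported twice from subsets and never once from everyone. Secondly, two columns headed with different treatment names invite a reader to see a treatment difference where none can exist.

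The SAP does pool elsewhere. Baseline characteristics (SAP 6.3) are shown by arm and for all subjects in the same FAS. The laboratory (SAP 11.3) and adverse event (SAP 11.2.3) summaries name All Subjects explicitly, and the adverse event summaries run past the point where the arms diverge.

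**Working it through.** **The plan's own figure.** N=45 comes from simulating and re-estimating a PK/PD model whose structure and parameters are not in the documents, so it cannot be reproduced. The split can: 45 × 2/3 = 30 and 45 × 1/3 = 15.

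**Inputs.** n = 15, 30 and 45 (Protocol 5.1.3); Wilson 95% intervals for responders (SAP 8.2.1), z = 1.96. Response rates are assumed, because none is given.

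**Is pooling valid?** Yes. Treatment is identical and allocation is random. LOCF only carries values forward, and NRI acts visit by visit, so no post-divergence data enter the Week 16 summaries.

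**Responder intervals.** With p = x/n, the Wilson limits are

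[p + z²/(2n) ± z √(p(1−p)/n + z²/(4n²))] / (1 + z²/n).

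For 36/45: the centre is (0.8 + 0.0427)/1.0854 = 0.776 and the half-width is 1.96 × √(0.003556 + 0.000474)/1.0854 = 0.115, giving 66.2% to 89.1%.

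| Assumed rate | n=15 | n=30 | n=45 |
|---|---|---|---|
| 40% | 19.8–64.3 (width 44.4) | 24.6–57.7 (33.1) | 27.0–54.5 (27.5) |
| 60% | 35.7–80.2 (44.4) | 42.3–75.4 (33.1) | 45.5–73.0 (27.5) |
| 80% | 54.8–93.0 (38.1) | 62.7–90.5 (27.8) | 66.2–89.1 (22.9) |

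Against arm B the pooled interval is 1 − 27.5/44.4 = 38% narrower at 40% or 60%, and 1 − 22.9/38.1 = 40% narrower at 80%. Against arm A the reductions are 1 − 27.5/33.1 = 17% and 1 − 22.9/27.8 = 18%.

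**Continuous means.** The 95% CI width is 2 t(0.975, n−1)/√n in SD units: 1.108, 0.747 and 0.601 for n = 15, 30 and 45. Pooling is 1 − 0.601/1.108 = 46% narrower than arm B and 1 − 0.601/0.747 = 20% narrower than arm A.

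**Risk of misreading.** I enumerated Binomial(30, p) × Binomial(15, p) exactly, with the same true rate in both arms.

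| True rate | Observed gap ≥ 20 points | Gap > 20 points | Wilson intervals do not overlap |
|---|---|---|---|
| 60% | 23.8% | 16.2% | 0.72% |
| 80% | 14.6% | 8.5% | 0.35% |

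The first two columns differ because a gap of exactly 20 points is an attainable value (6/30). A sizeable chance gap in the percentages is common; non-overlapping intervals are rare.

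**The case against.** The strongest reply is that nothing is lost, only not printed. Responder counts can be added across arms and put into the Wilson formula. SAP 3.1 prints n, mean and SD per arm and visit, from which the pooled mean, SD and t interval follow exactly. That is right, and it limits the point to what this SAP reports. It still leaves the reader to do the work for every endpoint and visit, and pooled medians and the pooled curve cannot be rebuilt from the summaries.

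Other points in the plan's favour:
- **By-arm display is the protocol's specification (14.3.1 to 14.3.2.2), and it shows comparability before divergence.** True, and a reason to keep those displays; it does not argue against an added column.
- **The study is exploratory and unpowered, and no between-arm test is planned.** True. Its efficacy output is then estimation with confidence intervals, where precision is what counts.
- **The study was sized for a PK/PD model that combines both arms with PS0010.** True. That model has its own data analysis plan and report, not available here, and it does not replace the secondary endpoint tables. The interim SAP was not available either.
- **Table 14-1 is a stated display choice.** In part. The table also leaves All Subjects blank for safety data although SAP 11.3 asks for that column, so it is not a reliable guide. The point rests on the section wording.
- **The gain over arm A, the larger arm, is only 17–20%, and each percentage is printed with its interval.** Both stand. The primary endpoint at Week 28 is untouched.

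**Conclusion.** The concern holds. Through the predose Week 16 assessment the two arms estimate the same quantities, and this SAP reports them only from subsets of about 30 and 15. For assumed response rates of 40% to 80%, the pooled Wilson interval is 38–40% narrower than arm B's and 17–18% narrower than arm A's; for means the figures are 46% and 20%. The percentages rest on the assumed rates and on the planned 30/15 split being achieved. The conclusion that the pooled estimate is more precise does not depend on the rate chosen.

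This is a reporting gap that costs precision. It creates no bias, and the by-arm tables remain correct. The misreading risk is confined to reading the percentages without their intervals. After the Week 16 injection, including flow cytometry at Week 36/SFU, by-arm display is the right one. The change is worth making because it is cheap and improves all four secondary endpoints.

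**What to change.** In SAP 8.1.2, 8.2, 8.3 and 9.2, and in Table 14-1, add an All Subjects column with 95% CI, and an All Subjects curve in the figures, for efficacy and flow cytometry visits up to and including predose Week 16. Keep all planned by-arm displays at every visit. Add a footnote that differences between arms through Week 16 cannot reflect the Week 16 dose.

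By-visit concentration and ADA summaries through predose Week 16 may follow the same rule. Overall ADA status (SAP 10) should not, because it uses visits after the arms diverge.

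**Cost.** One sentence, one footnote and one column or curve per affected output. That covers several tables: PASI by LOCF and observed cases, PASI and IGA response by NRI and observed cases, BSA, HADS and the flow cytometry variables. It is extra programming only. No new data are needed and no planned display changes. If the sponsor wants less, the four Week 16 secondary endpoints and the PASI course should come first.
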